14.2. Laboratory Safety Assessments

The following laboratory tests will be performed to evaluate the safety profile of ISIS 396443:

- Blood chemistry: total protein, albumin, creatinine, cystatin C, creatine phosphokinase, blood urea nitrogen, total bilirubin (direct and indirect), alkaline phosphatase, alanine aminotransferase, aspartate aminotransferase, glucose, calcium, phosphorus, chloride, sodium, potassium
- Hematology: red blood cells, hemoglobin, hematocrit, platelets, white blood cells, white blood cell differential
- Urinalysis: specific gravity, pH, protein, glucose, ketones, bilirubin, red blood cells, white blood cells, epithelial cells, bacteria, casts, crystals

CONFIDENTIAL

The information contained herein may not be used, disclosed, or published without the written consent of Biogen MA Inc.

15. SAFETY DEFINITIONS, RECORDING, REPORTING, AND RESPONSIBILITIES

Throughout the course of the study, every effort must be made to remain alert to possible AEs. If an AE occurs, the first concern should be for the safety of the subject. If necessary, appropriate medical intervention should be provided.

At the signing of the ICF, each subject's legally authorized representative and/or main caregiver(s) must be given the names and telephone numbers of study site staff for reporting AEs and medical emergencies.

15.1. Definitions

15.1.1. Adverse Event

An AE is any untoward medical occurrence in a patient or clinical investigation subject administered a pharmaceutical product and that does not necessarily have a causal relationship with this treatment. An AE can therefore be any unfavorable and unintended sign (including a clinically significant abnormal laboratory finding), symptom, or disease temporally associated with the use of a medicinal (investigational) product, whether or not related to the medicinal (investigational) product.

Determination of whether an abnormal laboratory value meets the definition of an AE will be made by the Investigator. Abnormal laboratory findings that are considered by the Investigator as not clinically significant should not be reported as AEs. Although abnormal laboratory values are typically not considered AEs, the following considerations may result in an abnormal laboratory value being considered an AE:

- A laboratory test result that meets the criteria for an SAE
- A laboratory test result that requires the subject to receive specific corrective therapy
- A laboratory abnormality that the Investigator considers to be clinically significant

15.1.2. Serious Adverse Event

An SAE is any untoward medical occurrence that at any dose:

- Results in death
- In the view of the Investigator, places the subject at immediate risk of death (a life-threatening event); however, this does not include an event that, had it occurred in a more severe form, might have caused death
- Requires inpatient hospitalization or prolongation of existing hospitalization. Hospitalization is defined as an admission of >24 hours to a medical facility and does not qualify as an AE
- Results in persistent or significant disability/incapacity

CONFIDENTIAL

The information contained herein may not be used, disclosed, or published without the written consent of Biogen MA Inc.

- Results in a congenital anomaly/birth defect

An SAE may also be any other medically important event that, in the opinion of the Investigator, may jeopardize the subject or may require intervention to prevent one of the other outcomes listed in the definition above. (Examples of such medical events include allergic bronchospasm requiring intensive treatment in an emergency room or convulsions occurring at home that do not require an inpatient hospitalization.)

15.1.3. Prescheduled or Elective Procedures or Routinely Scheduled Treatments

A prescheduled or elective procedure or a routinely scheduled treatment will not be considered an SAE, even if the subject is hospitalized; the study site must document all of the following:

- The prescheduled or elective procedure or routinely scheduled treatment was scheduled (or was on a waiting list to be scheduled) prior to obtaining consent from the subject's parent or legal guardian to participate in the study.
- The condition requiring the prescheduled or elective procedure or routinely scheduled treatment was present before and did not worsen or progress in the opinion of the Investigator between the subject's parent's or legal guardian's consent to participate in the study and the time of the procedure or treatment.
- The prescheduled or elective procedure or routinely scheduled treatment is the sole reason for the intervention or hospital admission.
 - If a subject is hospitalized due to local requirements for administration of the study treatment, the hospitalization should not be considered an SAE unless one of the requirements in Section 15.1.2 is met.

15.2. Safety Classifications

15.2.1. Investigator Assessment of Events

All events must be assessed to determine the following:

- If the event meets the criteria for an SAE as defined in Section 15.1.2
- The relationship of the event to study treatment as defined in Section 15.2.2
- The severity of the event as defined in Section 15.2.3

CONFIDENTIAL

The information contained herein may not be used, disclosed, or published without the written consent of Biogen MA Inc.

15.2.2. Relationship of Events to Study Treatment

The following definitions should be considered when evaluating the relationship of AEs and SAEs to the study treatment:

Relationship of Event to Study Treatment	
Related	There is clear evidence that the event is related to the use of the investigational drug (e.g., confirmation by positive re-challenge test).
Possible	The event cannot be explained by the subject's medical condition, concomitant therapy, or other causes, and there is a plausible temporal relationship between the event and administration of the investigational drug.
Unlikely/ Remote	An event for which an alternative explanation is more likely (e.g., concomitant medications or ongoing medical conditions) or the temporal relationship to investigational drug administration and/or exposure suggests that a causal relationship is unlikely. (For reporting purposes, Unlikely/Remote will be grouped together with Not Related.)
Not Related	The event can be readily explained by the subject's underlying medical condition, concomitant therapy, or other causes; therefore, the Investigator believes no relationship exists between the event and the investigational drug.

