3. SYNOPSIS

This is a brief summary. For details, refer to the body of the protocol.

Protocol Number: 232SM202

Protocol Title: A Phase 2, randomized, double-blind, sham-procedure controlled study to assess the safety and tolerability and explore the efficacy of ISIS 396443 (BIIB058) administered intrathecally in subjects with spinal muscular atrophy who are not eligible to participate in the clinical studies ISIS 396443-CS3B or ISIS 396443-CS4

Version Number: 4

Name of Study Treatment: Nusinersen (also known as BIIB058 and ISIS 396443)
Note: For the purposes of this protocol, when referring to “study drug,” Nusinersen will be used in place of ISIS 396443. When referring to the protocol title or previous (“index”) studies, ISIS 396443 will be used. The term “study treatment” refers to administration of Nusinersen or the sham procedure during the blinded portion of the study.

Study Indication: Spinal muscular atrophy (SMA)

Phase of Development: 2

Study Rationale: The rationale of Part 1 of the study is to assess the safety and tolerability and evaluate the utility of selected exploratory efficacy endpoints in subjects with SMA treated intrathecally with Nusinersen who are not eligible for the clinical studies ISIS 396443-CS3B or ISIS 396443-CS4.

Based on emergent data from the Nusinersen clinical development program, the Sponsor may decide to terminate Part 1 early, and all subjects may be offered the opportunity to transition to Part 2 (the open-label extension phase) prior to completion of all Part 1 evaluations. The rationale of Part 2 of the study is to assess the long-term safety and tolerability of Nusinersen in subjects with SMA who participated in Part 1 and completed their End of Part 1 Evaluation assessments.

Study Objectives and Endpoints: **Part 1**

Primary objective:

The primary objective of Part 1 of this study is:

- To assess the safety and tolerability of Nusinersen in subjects

CONFIDENTIAL

The information contained herein may not be used, disclosed, or published without the written consent of Biogen MA Inc.

with SMA who are not eligible to participate in the clinical studies ISIS 396443-CS3B or ISIS 396443-CS4.

The primary endpoints that relate to this objective are:

- Incidence of adverse events (AEs) and serious AEs (SAEs)
- Change from baseline in clinical laboratory parameters, electrocardiograms (ECGs), and vital signs
- Change from baseline in neurological examination outcomes

Secondary objective:

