15.2.2. Relationship of Events to Study Treatment

The following definitions should be considered when evaluating the relationship of AEs and SAEs to the study treatment:

CONFIDENTIAL

The information contained herein may not be used, disclosed, or published without the written consent of Biogen MA Inc.

Relationship of Event to Study Treatment	
Related	There is clear evidence that the event is related to the use of the investigational drug (e.g., confirmation by positive re-challenge test).
Possible	The event cannot be explained by the subject's medical condition, concomitant therapy, or other causes, and there is a plausible temporal relationship between the event and administration of the investigational drug.
Unlikely/ Remote	An event for which an alternative explanation is more likely (e.g., concomitant medications or ongoing medical conditions) or the temporal relationship to investigational drug administration and/or exposure suggests that a causal relationship is unlikely. (For reporting purposes, Unlikely/Remote will be grouped together with Not Related.)
Not Related	The event can be readily explained by the subject's underlying medical condition, concomitant therapy, or other causes; therefore, the Investigator believes no relationship exists between the event and the investigational drug.

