Study ISIS 396443-CS2 was an open-label, multiple-ascending dose, Phase 1/2a study designed to assess the safety, tolerability, and PK of ISIS 396443 in subjects with later-onset SMA. Multiple doses of ISIS 396443 were administered by intrathecal injection to subjects with SMA who were 2 to 15 years of age. Four dose levels (3, 6, 9, and 12 mg) were evaluated sequentially. Each dose level was studied in a cohort of 8 or 9 subjects, where all subjects received study treatment. The 6 subjects who participated in Cohort 1 of ISIS 396443-CS1 were eligible to enroll in ISIS 396443-CS2; 3 of these subjects enrolled in ISIS 396443-CS2 Cohort 1 and the other 3 enrolled in ISIS 396443-CS2 Cohort 2. Thirty-four subjects were enrolled, and all but 1 subject completed the study. One subject in the 12-mg ISIS 396443 dose cohort discontinued treatment early because of the Investigator's decision. The Investigator concluded that the subject and the parents could not tolerate the study procedures associated with dosing and PK draws, and thus, the subject was withdrawn. ISIS 396443 was well tolerated, and no safety concerns were reported when ISIS 396443 was administered as multiple doses up to 12 mg. Post lumbar puncture (LP) syndrome was the most commonly reported AE. None of the AEs reported during the study were considered related to ISIS 396443 or resulted in discontinuation from the study or of the study treatment. Three SAEs were reported during the study; all were assessed as unrelated to ISIS 396443. There were no clinically significant changes in vital signs, neurological or physical examination findings, or safety laboratory parameters related to ISIS 396443. There were no dose-related safety concerns.

Study ISIS 396443-CS10 was a single-dose open-label study to assess the safety and tolerability of a single intrathecal dose in subjects with later-onset SMA who participated in ISIS 396443-CS1 Cohorts 2, 3, and 4 (3, 6, or 9 mg). Eighteen subjects (4 subjects at 6-mg dose and 14 subjects at 9-mg dose) were enrolled and received study treatment. All 18 subjects completed the study.

CONFIDENTIAL

The information contained herein may not be used, disclosed, or published without the written consent of Biogen MA Inc.

Ongoing studies in subjects with SMA

ISIS 396443 is also being evaluated in 7 ongoing studies: ISIS 396443-CS3B, ISIS 396443-CS3A, 232SM201, ISIS 396443-CS4, ISIS 396443-CS12, ISIS 396443-CS11, and 232SM202 (the present study).

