15.3.4. Suspected Unexpected Serious Adverse Reactions

SUSARs are SAEs that are unexpected and judged by the Investigator or the Sponsor (or designee) to be related to the study treatment administered.

The Sponsor (or designee) will report SUSARs to the appropriate regulatory authorities and to Investigators as required, according to local law.

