#### **5.1.2 Adverse events by relationship to study treatment**

The investigator is to record the degree to which each AE is related to study drug (not related, unlikely or remotely related, possibly related, and related). If a subject experiences the same AE multiple times, the event with the strongest relationship to study drug will be counted. The incidence within each category will be presented. The incidence of drug-related events (those categorized as possibly related or related) will be summarized.

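### The relatedness scale has no grade for an adverse event that SMA and nusinersen explain about equally well, and it leaves open whether the lumbar puncture is part of what is being judged

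*Protocol*

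**What the plan says.** Protocol Version 4, Section 15.2.2, sets out four grades.

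- *Related* asks for this: "There is clear evidence that the event is related to the use of the investigational drug". A positive re-challenge is the example given.
- *Possible* has two conditions, and both must hold: "The event cannot be explained by the subject's medical condition, concomitant therapy, or other causes, and there is a plausible temporal relationship" to administration of the investigational drug.
- *Unlikely/Remote* applies when another explanation is the more probable one, or when timing or exposure speaks against the drug.
- *Not Related* applies when "The event can be readily explained by the subject's underlying medical condition, concomitant therapy, or other causes", so that the investigator sees no relationship at all.

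The section merges the last two grades for reporting.

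The heading and lead-in ask about study treatment, a term that, according to the Synopsis, "refers to administration of Nusinersen or the sham procedure during the blinded portion of the study". All four rows nevertheless name the investigational drug. SAP 5.1.2 has the investigator grade against study drug and adds: "The incidence of drug-related events (those categorized as possibly related or related) will be summarized". SAP 5.1.6 tabulates the four grades separately in the integrated analysis and plans a table and listing of events following the dosing procedure or LP.

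The grade is used again in two places. Section 15.3.4 defines SUSARs as serious events that are "unexpected and judged by the Investigator or the Sponsor (or designee) to be related to the study treatment administered". Under Section 15.3.3, an SAE after the final follow-up is reported only if the investigator considers it related.

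**The concern.** Children with symptomatic SMA have many events that the disease could explain; Protocol Section 5.1 describes respiratory failure as the usual course of the severe form. If the mere availability of such an explanation rules out *Possible*, the drug-related incidence is held down by the wording of the scale and not by the evidence. Safety is the primary objective, and Protocol Section 16.2.2.2 plans AE incidence by relationship. Part 2 has no concurrent control, and the scheduled DSMB reviews cover Part 1 only, so individual causality judgements carry more weight there.

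The second problem is the object of the judgement. Nusinersen is given by lumbar puncture, while the sham is a needle prick without one (Section 11.1.2). Procedure effects therefore differ between the arms, yet no row says how to grade them.

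**Working it through.** The plan states no figure for this point, so there is none to reproduce. The check is to set the definitions side by side and follow the grade to where it is used.

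**1. Which definition is met?** Take an event with plausible timing and no proof such as re-challenge.

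| Standing of the other explanation | Possible | Unlikely/Remote | Not Related |
|---|---|---|---|
| None exists | met | not met | not met |
| Exists, about as likely as the drug | not met: the event can be explained | not met: the alternative is not more likely | not met: the investigator does not believe there is no relationship |
| Exists, more likely than the drug | not met | met | only if it readily explains the event |
| Clearly accounts for the event | not met | met | met |

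*Related* is not met in any row, because clear evidence is lacking. The second row has no grade. An investigator who must tick a box, and who has just found *Related* and *Possible* excluded, is left with the two grades that are merged as unrelated. This is pressure in one direction, not a rule.

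**2. What is being judged?** Read by the rows, a lumbar-puncture complication has another cause, the procedure, and fails *Possible*. Read by the heading and the Synopsis definition, administration belongs to the study treatment, and the same complication could be graded related. The text supports both readings. Section 15.3.1 mentions relationship to the injection or the sham procedure, but Section 15.2.2 has no row for that judgement. For a sham subject in Part 1 the rows ask about a drug the child never received.

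**3. Where does the grade reach?**

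- Affected: the drug-related and by-relationship tables (SAP 5.1.2 and 5.1.6), including the related-event lines of the Part 2 overall summary.
- Partly affected: SUSAR classification, because the sponsor may also judge an event related.
- Affected: SAE reporting after the last visit.
- Not affected: recording of AEs (Section 15.3.1), incidence of all AEs and SAEs, and the procedure/LP table.

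**4. Illustration, on assumed rates.** Suppose a respiratory event occurs in 40% of children without a drug effect and in 60% on nusinersen, with the planned 14 and 7 children.

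- Nusinersen cases: 0.60 × 14 = 8.4.
- Excess due to the drug: (0.60 − 0.40) × 14 = 2.8.
- Drug-related count: from 0, if every investigator treats SMA as explaining every case, to 8.4, if every case is graded *Possible*.
- All-AE table: 8.4 of 14 (60%) against 0.40 × 7 = 2.8 of 7 (40%), whatever the grades.

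The drug-related count can lie anywhere in that range. The current wording pulls it towards the lower end.

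**The case against.** The strongest reply is that the definitions are offered for consideration and are not an algorithm. No rule sends an ambiguous event to *Not Related*, and that grade also requires a belief that no relationship exists. This stands: a reader might infer that such events are counted as unrelated, but the documents show only a gap and a push.

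A reader might also infer that lumbar-puncture complications disappear, or that the scale names nothing but the drug. Neither is supported. The heading's term covers administration, every AE is recorded, and SAP 5.1.6 plans a procedure/LP table. What that table does not provide is a causal judgement.

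The protocol's summary of Study CS2 (Section 5.3.2) is tempting as proof: post-LP syndrome was its most frequent event, yet no event was attributed to nusinersen. It was a different study, its scale is not stated, and finding post-LP syndrome unrelated to the drug may simply be correct. In CS1, two events were judged related to the drug.

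It is also fair to say that a real excess would show elsewhere. The primary endpoint is incidence of all AEs and SAEs, and the integrated safety displays (SAP Section 2) keep a sham Part 1 column. That column is not concurrent with Part 2. For SUSARs, the sponsor can judge independently, and every on-study SAE is reported within 24 hours whatever its grade (Section 15.3.3). These points limit the consequence but repair neither the gap nor the mismatch between heading and rows.

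**Conclusion.** The point holds as a defect of definition. An event about equally compatible with SMA and nusinersen has no grade, and the remaining choices favour the unrelated group. The object of the judgement is also stated in two ways. The direction of the effect is towards a lower drug-related incidence. Its size cannot be derived from the documents, because it depends on how often such events occur and how literally investigators apply the wording.

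The illustrative zero is an extreme that requires every investigator to treat SMA as explaining every case; it is not a forecast. The comparison of all AEs and SAEs is not biased by this, so the primary safety endpoints stand. A reader might conclude that relatedness is the main evidence on causality in Part 2. The documents do not show that: the Part 2 AE outputs are mainly incidence of all AEs and SAEs, with relatedness only in the overall summary.

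**What to change.** 1. In Section 15.2.2, reword *Possible* to: plausible temporal relationship, and no alternative explanation is more likely than the study treatment. Limit *Not Related* to events for which the alternative clearly accounts for the event. With *Unlikely/Remote* left as it is, the second row of the table above then falls under *Possible* and the gap closes. A looser test, under which any cause that cannot be ruled out counts as *Possible*, would go too far: almost every event with plausible timing would qualify.
2. Replace the drug in the rows with study treatment, and record two separate attributions, one to the drug and one to the dosing procedure (lumbar puncture or sham).
3. Tabulate each attribution in SAP 5.1.2 and 5.1.6.
4. Reconcile the protocol's merging of *Unlikely/Remote* with *Not Related* with the four separate categories in SAP 5.1.6.

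The cost is protocol and SAP wording, one CRF field and a note to sites. The drug-related figure will look slightly less favourable. Part 1 has stopped and Part 2 is ending early (SAP Sections 1 and 1.3), so many events will already have been graded. They should be shown separately from those graded under the new wording, because up to 21 children are too few to absorb a silent change of scale.

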15.2.3. Severity of Events

The following definitions should be considered when evaluating the severity of AEs and SAEs:

Severity of Event	
Mild	The event is easily tolerated by the subject and does not affect the subject's usual daily activities.
Moderate	The event causes the subject more discomfort and interrupts the subject's usual daily activities.
Severe	The event is incapacitating and causes considerable interference with the subject's usual daily activities.

15.2.4. Expectedness of Events

Expectedness of all AEs will be determined by the Sponsor (or designee) according to the Investigator's Brochure.

15.3. Monitoring and Recording Events

15.3.1. Adverse Events

For subjects who receive study treatment, any AE experienced between the time of signing the ICF and Part 2 Final Follow-up Evaluation/Telephone Call (or End of Part 1 Evaluation, if the subject does not enroll in Part 2) will be recorded on the CRF, regardless of the severity of the event or its relationship to study treatment injection or sham procedure. For subjects who never receive study treatment, no AEs need to be recorded on the applicable CRF.

CONFIDENTIAL

The information contained herein may not be used, disclosed, or published without the written consent of Biogen MA Inc.

